6.1 CRITERIA FOR SUBJECT ELIGIBILITY

6.2 Subject Inclusion Criteria

- Patients must have a diagnosis of T- or NK-cell NHL with one of the following subtypes: Blastic NK cell lymphoma; NK/T-cell lymphoma/leukemia; Adult T-cell lymphoma/leukemia; T-cell PLL; T-lymphoblastic lymphoma; Peripheral T-cell lymphoma, not otherwise specified; Angioimmunoblastic T-cell lymphoma; Anaplastic large cell lymphoma; transformed mycosis fungoides; Subcutaneous panniculitis-like T-cell lymphoma; Nasal T/NK cell lymphoma; Enteropathy-type T-cell lymphoma; Hepatosplenic γ/δ T-cell lymphoma.
- Patients must have been previously treated with cytotoxic chemotherapy and/or monoclonal antibody and be without a standard curative treatment option. For the purposes of this trial, allogeneic bone marrow transplantation is not considered a standard curative option.
- Patients must be off any other therapy such as interferon, antibody therapy, retinoids, or other non-chemotherapeutic treatments for ≥ 3 weeks prior to beginning treatment on study. Stable doses of corticosteroids will be allowed.
- Patient must be off any conventional chemotherapy or radiation therapy (encompassing a substantial [$>10\%$] amount of bone marrow) within 4 weeks (6 weeks for nitrosoureas or mitomycin C) prior to study.
- Good performance status (ECOG 0 – 2)
- Age ≥ 2 years.
- Patients must have adequate organ and marrow function as defined below:

Phase I eligibility criteria

- absolute neutrophil count $\geq 1,500/uL$
- platelets $\geq 100,000/uL$
- serum creatinine ≤ 1.0 mg/dL or estimated GFR > 60 ML/min
- total bilirubin ≤ 2.0 X normal institutional limits
- AST (SGOT)/ALT (SGPT) ≤ 2.5 X institutional upper limit of normal

Phase II eligibility criteria

- absolute neutrophil count $\geq 500/uL$
- platelets $\geq 50,000/uL$
- serum creatinine < 2.0 mg/dL*
- total bilirubin ≤ 2.0 X normal institutional limits*
- AST (SGOT)/ALT (SGPT) ≤ 2.5 X institutional upper limit of normal*

**Sponsor: Memorial Sloan-Kettering Cancer Center
IRB Protocol**

IRB#: 06-065A(4)

*For the phase II portion of the study, the investigator may make an exception if the laboratory abnormality is due to lymphoma.

- For the phase I portion of the trial, patients must have **evaluable** disease.
- For the phase II portion of the trial, patients must have measurable disease defined as any nodal site or mass lesion ≥ 1.5 cm in longest transverse diameter on physical exam or computed tomography scan or a measurable extranodal site > 1 cm.
- For patients with primarily blood or marrow based disease, evaluable patients will be eligible
- Signed informed consent and/or assent.

6.3 Subject Exclusion Criteria

- Active infections requiring antibiotics.
- Pregnant or lactating women. (Women and men of childbearing age should use effective contraception).
- New York Heart Association class III/IV congestive heart failure
- Patients seropositive for infection with Human Immunodeficiency virus (HIV-1) are excluded from the study because of the potential for serious infectious complications associated with a T-cell suppressive therapy in these patients.
- Concurrent active malignancy requiring therapy (other than a synchronous T/NK-cell NHL).
- Receipt of systemic corticosteroids within 7 days of study treatment, unless patient has been taking a continuous dose of no more than 10mg/day of prednisone for at least 1 month.
- Other serious or life-threatening condition(s) deemed unacceptable by the principal investigator.

Please note copies of source documentation confirming eligibility for patients enrolling at outside institutions must be provided to the MSKCC CTO registrar at the time of registration. Please fax to [contact] and PPR [contact]/[name].

**IRB
PB**

Amended: 8/26/08

**Sponsor: Memorial Sloan-Kettering Cancer Center
IRB Protocol**

IRB#: 06-065A(4)

7.0 RECRUITMENT PLAN

Recruitment Plan

Potential research subjects will be identified by a member of the patient's treatment team, the protocol investigator, or research team at Memorial Sloan-Kettering Cancer Center (MSKCC-Lead Center), University of Rochester Medical Center, and The Cleveland Clinic. If the investigator is a member of the treatment team, s/he will screen their patient's medical records for suitable research study participants and discuss the study and their potential for enrolling in the research study. Potential subjects contacted by their treating physician will be referred to the investigator/research staff of the study.

8.1 PRETREATMENT EVALUATION

The following tests are required prior to beginning therapy:

Within 2 weeks prior to starting on protocol:

- Relevant history and physical exam.
- The following blood tests will be required: CBC with differential, comprehensive profile, phosphorous, uric acid, LDH, PT and PTT.
- Urinalysis
- Urine or serum pregnancy test for woman with childbearing potential.

Within 1 month prior to starting on protocol:

- Bone marrow biopsy for histology and immunohistochemistry.
- Chest X-ray
- EKG
- Echocardiogram or MUGA
- CT scan of the chest, abdomen and pelvis.
- CT scan or MRI of relevant extranodal sites not included in chest, abdomen, and pelvis. (e.g. nasopharynx)
- PET scan (not required but encouraged)
- HIV test
- Hepatitis B surface antigen and antibody
- Hepatitis C antibody

**IRB
PB**

Amended: 8/26/08

- HTLV-1 antibody

9.1 TREATMENT/INTERVENTION PLAN

9.2 Pre-treatment Procedures

- Pretreatment laboratory evaluation: CBC with differential, Cr, AST, ALT, Alk Phos, Bili
- Premedication: Standard anti-emetics for a moderately emetogenic medication will be given. Hydrocortisone 100 mg/m² will be administered 30 minutes prior to each dose of clofarabine on cycles 1 and 2.
- Prehydration: 500 mL NS IV over 30-60 minutes.

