A decrease in left ventricular systolic function of unclear etiology has been observed in pediatric acute leukemia patients (n=55) treated with clofarabine at the 52 mg/m²/d dose level. In the phase II study (unpublished data)[28], the change in systolic function was transient in the majority of cases. On close inspection, the timing of the decrease in systolic function coincided with other clinical events such as sepsis and may have been related to either the clinical event itself or the drug(s) used to treat the problem. Unfortunately, in some cases, the decrease of LV function occurred when clofarabine was given within 6 months of the last anthracycline dose, making it impossible to determine if the decline was related to clofarabine or to the prior anthracycline therapy. Of note, clofarabine was given to one child with preexisting severe LV dysfunction with no significant further deterioration.

Small pericardial effusions were a frequent finding. They did not result in any significant hemodynamic effect and required no intervention. They were detected more frequently in the initial patients entered on the trial and the effusions were almost absent in the later patients. This may reflect changes in the protocol made to accommodate the fluid retention seen in the early patients [28].

Capillary leak syndrome also occurred rarely in 4 out of 60 pediatric leukemia patients [28]. Again, all of the pediatric patients were treated at the 52 mg/m²/d dose. There were 2 patients who had grade 4 capillary leak syndrome which resulted in death and may have been from the study drug. There was one patient had a grade 3 adverse event. Concurrent medical conditions such as sepsis and/or disease progression may have made these patients susceptible to this toxicity.

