In this study, the starting dose of 4 mg/m²/d for 3 consecutive days was chosen based on the MTD for both solid and lymphoproliferative disorders. In all of the published clofarabine trials, patients were treated for 5 consecutive days. With a MTD of 2 mg/m²/d, patients with solid and lymphoproliferative disorders received a weekly total dose of 10 mg/m²/wk. With a starting dose of 4 mg/m²/d for 3 consecutive days, patients will receive 12 mg/m²/wk. We predict that the DLT will occur around the third dose level since it is defined differently compared to the prior trials. The DLT, in this study, is defined in terms of delayed count recovery rather than grade 3 or 4 myelosuppression at any time following treatment.

IRB
PB

Amended: 8/26/08

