9.4 Supportive Medication (standard)

- **Sulfamethoxazole-trimethoprim DS bid will be administered for three consecutive days each week (typically Monday, Tuesday, and Wednesday)** as pneumocystis carinii pneumonia (PCP) prophylaxis. Patients who are allergic to sulfa may receive alternate prophylaxis such as aerosolized pentamidine 300 mg once per month. PCP prophylaxis will begin with the first cycle of chemotherapy.
- **Acyclovir 400 mg po bid or the renally adjusted equivalent will be administered as prophylaxis against Herpes Zoster.** It will begin with the first cycle of chemotherapy.
- Darbepoietin or erythropoietin may be administered as per hospital policy. Discontinuation of either of these medications or increasing the dose is based on standard dose and response criteria.
- Growth colony stimulation factor should be administered beginning 24-72 hours after the conclusion of each 3 day treatment cycle. The type and dose of the growth colony stimulation factor will be determined as per hospital policy.

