17.1 PROTECTION OF HUMAN SUBJECTS

Inclusion of Children in Research

Clofarabine is approved for the treatment of pediatric leukemia and this protocol includes children over the age of 2 years.

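### Children from age 2 are eligible, but prehydration, sulfamethoxazole-trimethoprim and acyclovir are ordered in fixed amounts with no scaling for body size (minor, patient safety)

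*Combined protocol and SAP*

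**What the plan says.** Section 6.2 sets the lower age limit at 2 years and provides for assent as well as consent. Section 17.1 states that "this protocol includes children over the age of 2 years". Its wording differs slightly from 6.2, but a 2-year-old qualifies under the inclusion criterion.

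The supportive orders are these:

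- Section 9.2: "Prehydration: 500 mL NS IV over 30-60 minutes". No frequency is given, so the figures below are per prehydration.
- Section 9.4, pneumocystis prophylaxis: "Sulfamethoxazole-trimethoprim DS bid will be administered for three consecutive days each week".
- Section 9.4, zoster prophylaxis: "Acyclovir 400 mg po bid or the renally adjusted equivalent will be administered as prophylaxis against Herpes Zoster". The only adjustment named is renal.

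Other items are scaled or deferred. Hydrocortisone in 9.2 and clofarabine in Table 9.0 are per m². For growth factor, 9.4 says "The type and dose of the growth colony stimulation factor will be determined as per hospital policy". No section gives a pediatric rule for the three fixed items.

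**The concern.** Eligibility spans toddlers to adults, but three orders are written as a single amount for all. Followed literally, the smallest patients receive the largest amount relative to body size, and the saline goes in within 30-60 minutes.

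Fluid handling matters for this drug. Section 5.2 reports frequent small pericardial effusions in children given clofarabine, and capillary leak syndrome in 4 of 60 children with leukemia. Two of those cases were grade 4, ended in death and were possibly due to the drug. On the effusions becoming rarer in later patients, it remarks: "This may reflect changes in the protocol made to accommodate the fluid retention seen in the early patients". The protocol's own background thus gives a reason for caution with fluid in children, and the order does not reflect it.

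What is at stake is the safety of a few small patients and a clear instruction for the participating sites.

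**Working it through.** **Inputs from the documents.** Minimum age 2 years (6.2); prehydration 500 mL (9.2); acyclovir 400 mg twice daily, so 800 mg per day (9.4). The plan states no per-m² figure for these items, so there is none to reproduce.

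**Inputs assumed.** Body surface area (BSA), because the documents give no body sizes: adult 1.6-2.0 m²; age 2, 0.50-0.60; age 5, 0.70-0.78; age 8, 0.90-1.00; age 12, 1.20-1.40.

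**Formulas.** Saline load = 500 / BSA. Ratio of child to adult load = adult BSA / child BSA, with the minimum from the smallest adult and largest child, and the maximum from the largest adult and smallest child.

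**Adult load.** 500/2.0 = 250 and 500/1.6 = 312.5, so 250-313 mL/m².

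| Age | Load, mL/m² | Ratio to adult |
|---|---|---|
| 2 | 500/0.60 = 833 to 500/0.50 = 1000 | 1.6/0.60 = 2.7 to 2.0/0.50 = 4.0 |
| 5 | 500/0.78 = 641 to 500/0.70 = 714 | 1.6/0.78 = 2.1 to 2.0/0.70 = 2.9 |
| 8 | 500/1.00 = 500 to 500/0.90 = 556 | 1.6/1.00 = 1.6 to 2.0/0.90 = 2.2 |
| 12 | 500/1.40 = 357 to 500/1.20 = 417 | 1.6/1.40 = 1.1 to 2.0/1.20 = 1.7 |

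**Acyclovir.** At age 2, 800/0.60 = 1333 to 800/0.50 = 1600 mg/m² per day. In an adult, 800/2.0 = 400 to 800/1.6 = 500 mg/m² per day. The ratio is again 2.7-4.0, as it is for any fixed dose, including sulfamethoxazole-trimethoprim.

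**Exposure behind the pediatric safety reports.** Those children received 52 mg/m²/day. The top level in Table 9.0 is 49 mg/m²/day for 3 days, or 3 × 49 = 147 mg/m² per course. If the children were treated for 5 days, their course was 5 × 52 = 260 mg/m². Five days is an assumption, because Section 5.2 says only that "In all of the published clofarabine trials, patients were treated for 5 consecutive days", and it cites the pediatric phase II cardiac data as unpublished. The reports therefore come from higher exposure than this trial plans.

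**The case against.** The strongest reply is that no harm is shown. Every ratio rests on assumed body sizes, the 2-year-old is the extreme case, and the excess is small by age 12. The expected number of children is not given; accrual is projected from the Lymphoma Service at 1-2 eligible patients a month, so very young patients may be rare. Section 6.3 excludes NYHA class III/IV heart failure, and Section 8.1 requires a baseline echocardiogram or MUGA. Section 9.4 is headed as standard care, and staff may adjust doses in practice.

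Most of this stands, and it is why the point is minor. It does not repair the order. Explicit amounts follow the heading in 9.4, and Section 7.0 names three recruiting centers. At any of them, a sensible adjustment for a small child would depart from the written instruction.

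Three stronger readings are tempting but unsupported:

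- **That children would be overdosed or harmed.** The documents give no safe pediatric limit for saline or either drug. Section 5.2 ties no event to prehydration, does not describe the earlier protocol changes, says the effusions needed no intervention, and names sepsis and progression as possible contributors to capillary leak.
- **That the maximum tolerated dose would be biased.** This needs a small child in phase I, a toxicity caused by saline or prophylaxis, and that toxicity being counted. The rule table in 14.4.2 counts drug-related events, so an event attributed to saline may not count. The chain is speculative.
- **That pentamidine needs the same scaling.** Section 9.4 offers it only as an example: "Patients who are allergic to sulfa may receive alternate prophylaxis such as aerosolized pentamidine 300 mg once per month". It is inhaled, and nothing in the documents supports dosing it by body surface.

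**Conclusion.** The point holds as a minor patient-safety correction. Three orders (prehydration, sulfamethoxazole-trimethoprim and acyclovir) are fixed for a population that deliberately includes children from age 2, and no section scales them for size or refers them to pediatric standards. On the assumed body sizes, a 2-year-old receives 2.7-4.0 times the adult amount per m², with the gap narrowing steadily with age. That the orders are unscaled comes directly from the text; only the size of the gap depends on the assumptions. Sample size, error rates, endpoints and analysis are unaffected.

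**What to change.** Leave eligibility and adult dosing as they are, and add two sentences.

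- Section 9.2: 'For patients under 18 years, prehydration volume and rate are set by weight or body surface area per institutional pediatric standards, maximum 500 mL.'
- Section 9.4: 'For patients under 18 years, sulfamethoxazole-trimethoprim and acyclovir are dosed per institutional pediatric standards, not exceeding the adult doses above.'

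The age limit settles which rule applies, and the caps keep any child from exceeding the adult amount. Deferring to institutional standards follows what 9.4 already does for growth factor. A specific mL/m² figure should not be written in, because the documents offer no clinical source for one.

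The cost is a two-sentence amendment sent to the participating sites.

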9.3 Clofarabine

Clofarabine will be infused intravenously over 1 hour and will be administered daily for 3 consecutive days. In the phase I portion of this study, the dose levels will be determined by the dose escalation schema in Table 9.0. Cycles will be repeated as early as day 22 ± 2 days or up to 2 weeks later (or 36 ± 2 days) if the patient meets retreatment criteria as defined in section 9.4.

Table 9.0 Dose Escalation Schema

Dose Level	Dose (mg/m ² /day)	% Increase	Multiple of Initial Dose
1	4	-	-
2	8	100	2.0 n
3	13.2	67	3.3 n
4	20	50	5.0 n
5	28	40	7.0 n
6	36	33	9.0 n
7	49	28	12.3 n

Refer to Section 14.1 for more details regarding dose escalation. Once the MTD of clofarabine has been identified, the remainder of the patients will be accrued to the phase II portion of the study.

Sponsor: Memorial Sloan-Kettering Cancer Center
IRB Protocol

IRB#: 06-065A(4)

9.4 Supportive Medication (standard)

- **Sulfamethoxazole-trimethoprim DS bid will be administered for three consecutive days each week (typically Monday, Tuesday, and Wednesday)** as pneumocystis carinii pneumonia (PCP) prophylaxis. Patients who are allergic to sulfa may receive alternate prophylaxis such as aerosolized pentamidine 300 mg once per month. PCP prophylaxis will begin with the first cycle of chemotherapy.
- **Acyclovir 400 mg po bid or the renally adjusted equivalent will be administered as prophylaxis against Herpes Zoster.** It will begin with the first cycle of chemotherapy.
- Darbepoietin or erythropoietin may be administered as per hospital policy. Discontinuation of either of these medications or increasing the dose is based on standard dose and response criteria.
- Growth colony stimulation factor should be administered beginning 24-72 hours after the conclusion of each 3 day treatment cycle. The type and dose of the growth colony stimulation factor will be determined as per hospital policy.

9.5 Re-treatment criteria

Patients will receive additional cycles of clofarabine as long as they meet the following criteria **at the time of re-treatment:**

- $ANC \geq 1000$ cell/ μ l (or $ANC \geq 500$ / μ l for patients who were enrolled at this level in the phase II portion of the trial only)
- Platelet $\geq 75,000$ / μ l (or platelet $\geq 50,000$ / μ l for patients who were enrolled at this level in the phase II portion of the trial only)
- Non-hematologic toxicity: if the toxicity is less severe than a grade 4 infection and/or a grade 4 hemorrhage, and it resolves to \leq grade 1 or baseline as per CTCAE v3.0 toxicity criteria at the time of retreatment.

Repeat cycles of clofarabine are administered on approximately a 21 day schedule unless the patient does not meet re-treatment criteria as defined above. For those patients who do not meet the above parameters at the day 22 ± 2 evaluation, their next cycle of therapy may be held up to 2 weeks. After any treatment delay, the patient will be re-evaluated the following week (up to day 36 ± 2 days). If the patient meets re-treatment criteria at the next evaluation, the next cycle of clofarabine will be administered at the full dose. If the patient does not meet re-treatment criteria at both the day 29 ± 2 and the day 36 ± 2 evaluation, this patient will be **removed** from the study **unless there has been a prior documented response (CR or PR) to therapy.**

**Sponsor: Memorial Sloan-Kettering Cancer Center
IRB Protocol**

IRB#: 06-065A(4)

In these cases, patients must meet all of the criteria defined in section 9.8. The dose of clofarabine will then be adjusted accordingly.

9.6 Interim Laboratory Evaluation

- weekly cbc with differential in the first cycle; then evaluation every 1 - 2 weeks, as indicated
- weekly comprehensive profile in the first cycle; then evaluation every 1 - 2 weeks, as indicated

9.7 Restaging

9.6.1 Following each course of clofarabine (every 2 cycles)

- CT scan of chest/abdomen/pelvis
- CT scan or MRI of relevant extranodal sites not included in the CT of the chest/abdomen/pelvis
- PET scan encouraged if previously positive

9.6.2 End of study

- CT scan of chest/abdomen/pelvis
- CT scan or MRI of relevant extranodal sites not included in the CT of the chest/abdomen/pelvis
- PET scan encouraged if previously positive
- Bone Marrow biopsy (if previously positive and if patient is in CR by other criteria)
- Echocardiogram if the dose of the clofarabine is ≥ 28 mg/m²/day

9.7 Treatment beyond 2 cycles

9.7.1 Following 2 cycles of clofarabine

Patients with stable disease, a partial response, or a complete response will receive 2 more cycles of clofarabine.

9.7.2 Following 4 cycles of clofarabine

Patients with a partial response or a complete response will receive 2 more cycles of clofarabine. Patients may be treated up to 2 cycles beyond their maximum response.

**Sponsor: Memorial Sloan-Kettering Cancer Center
IRB Protocol**

IRB#: 06-065A(4)

9.7.3 Progression of disease

Patients with progression of disease at any time will be declared treatment failures and removed from the study.

9.8 Dose reduction

Patients can be retreated with clofarabine at a reduced dose if all the following conditions are met:

- Clinical or radiologic response (PR or CR)
- The non-hematologic toxicities in the prior cycle were not a life-threatening infection or hemorrhage
- Re-treatment criteria have been met as defined in section 9.4

Determination of Dose

If the above conditions are met, patients will be treated at the next lower dose level.

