4.3 Intervention

Patients will receive intravenous clofarabine once daily for three consecutive days. Doses of clofarabine will start at 4 $\text{mg}/\text{m}^2/\text{day}$ and will be escalated to higher dose levels as described in Section 9.2. If the toxicity criteria have not been exceeded at the day 22 \pm

**IRB
PB**

Amended: 8/26/08

**Sponsor: Memorial Sloan-Kettering Cancer Center
IRB Protocol**

IRB#: 06-065A(4)

2 evaluation, the next course of therapy will be administered. Interim restaging, as defined in Section 9.6, will be performed at the conclusion of 2 cycles of clofarabine. The dose-limiting toxicities will be based on the **first** cycle of therapy.

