10.0 EVALUATION DURING TREATMENT/INTERVENTION

- 10.1 Prior to each cycle of chemotherapy, the patient will have an interval history, toxicity evaluation and physical examination, including vital signs, and performance status.
- 10.2 CBC with differential, and comprehensive profile will be required prior to each cycle of chemotherapy.
- 10.3 After completion of 2 cycles of clofarabine, the patient will be assessed or reassessed for response as per section 9.6.
- 10.4 If the patient has achieved a complete response (CR), a repeat bone marrow biopsy will be performed only in those cases where it had been previously positive.
- 10.5 Following completion of the treatment plan, responding patients should be followed at three month intervals for the first two years post-therapy to document duration of response.

**Sponsor: Memorial Sloan-Kettering Cancer Center
IRB Protocol**

IRB#: 06-065A(4)

Table 10.0 Study Calendar

Assessments	Pre-treatment		Day 1 Cycle 1	Day 8 Cycle 1	Day 15 Cycle 1	Day 22, 29, 36 Cycle 1 ^a	Day 1 Cycle 2	Day 8 Cycle 2	Day 15 Cycle 2	Day 22, 29, 36 Cycle 2 ^a	Off study/ Cont Rx
	≤ 30 days prior to Rx	≤ 14 days prior to Rx									
Clofarabine			XXX				XXX				
Informed consent and/or assent		X									
Medical history and height (cm)		X									
Interval history, incl. AE eval. and med list		X	X			X	X			X	X
PE, VS, incl. wt and ECOG PS		X	X			X	X			X	X
Cbc with differential		X	X	X	X	X	X		X	X	X
Serum chemistry ^b		X	X	X	X	X	X		X	X	X
LDH		X									X
Coagulation profile / urinalysis		X									
Beta-HCG ^c		X									
Viral serologies ^d	X										
EKG	X										X
Echo or MUGA	X										X ^e
Chest Xray	X										
Tumor imaging ^f	X										X
Bone marrow biopsy	X										X ^g

^aIf the re-treatment criteria is not met at the day 22 ± 2 day evaluation, the treatment will be withheld and the patient will be re-evaluated the following week(s), up day 36 ± 2 days from the beginning of therapy.

^bSerum chemistry: albumin, alkaline phosphatase, total bilirubin, bicarbonate, BUN, calcium, chloride, creatinine, glucose, phosphorus, potassium, total protein, SGOT (AST), SGPT (ALT), sodium, magnesium, uric acid

^cSerum or urine beta-HCG is required for all women of childbearing potential.

^dViral serologies: HIV, Hep B S Ag, Hep B S Ab, Hep C Ab, HTLV-1

^eEchocardiogram/MUGA: A followup echocardiogram or MUGA must be ordered if the dose level is at or above 28 mg/m²/d

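### A patient who recovers from a cycle-1 non-hematologic DLT but has no documented response can only repeat the same dose or stop, because section 9.8 ties dose reduction to a PR or CR

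*Combined protocol and SAP*

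**What the plan says.** Section numbers here follow the headings in the body; some internal cross-references are off by one (9.8 cites the re-treatment criteria as 9.4, but they are headed 9.5).

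- **DLT.** Section 14.5 counts any non-hematologic toxicity of grade 3 or higher, and platelets below 75,000 persisting to about day 36. Section 4.3 sets the window: "The dose-limiting toxicities will be based on the" first cycle.
- **Clearance for the next cycle.** Section 9.5 accepts a non-hematologic toxicity "if the toxicity is less severe than a grade 4 infection and/or a grade 4 hemorrhage", provided it has settled to grade 1 or lower or to baseline and counts have recovered. It does not mention DLT.
- **Dose after a delay.** Section 9.5: "If the patient meets re-treatment criteria at the next evaluation, the next cycle of clofarabine will be administered at the full dose".
- **Dose at day 22.** Section 4.3 says that, if the toxicity criteria were not exceeded at the day 22 "evaluation, the next course of therapy will be administered". It names no dose.
- **No recovery.** Section 9.5: "If the patient does not meet re-treatment criteria at both the day 29" and the day 36 visit, the patient is removed. The exception is a patient with a documented CR or PR, who is referred to 9.8 for a dose adjustment.
- **Reduction.** Section 9.8: "Patients can be retreated with clofarabine at a reduced dose if all the following conditions are met". The first condition is "Clinical or radiologic response (PR or CR". The others exclude a life-threatening infection or hemorrhage in the prior cycle and require the re-treatment criteria to be met. The reduction is one dose level.
- **Response timing.** Item 10.3: "After completion of 2 cycles of clofarabine, the patient will be assessed or reassessed for response as per section 9.6". Section 12.2 likewise assesses response every 2 cycles.
- **Investigator discretion.** Section 13.0 permits removal for unacceptable toxicity or in the patient's best interest. It does not mention a lower dose.

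**The concern.** Dose reduction in this plan depends on benefit, not on toxicity. A patient who has had a drug-related DLT and recovered would commonly step down one level. Here that step needs a response which, on the schedule, cannot normally be documented before cycle 2 is given. What remains is to repeat the dose that caused the DLT or to stop.

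The gap continues past cycle 2. Sections 4.4 and 9.7.1 allow cycles 3 and 4 in stable disease, and such a patient still has no reduction available.

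The events in question can be serious. Section 5.2 reports grade 4 hepatic toxicity in 3 adults at 40 mg/m²/d and, in children at 52 mg/m²/d, capillary leak syndrome with two deaths that may have been drug-related. Those were 5-day schedules, but Table 9.0 escalates to 49 mg/m²/d for 3 days and children from age 2 are eligible. A hepatic event that settles is not among the toxicities that bar re-treatment. Removing the patient instead gives up possible benefit in a population that section 6.2 requires to be without a standard curative option.

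**Working it through.** The plan states no figure on this point, so there is none to reproduce. The check is a trace of the rules, followed by an estimate of scale.

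**Rule trace for a cycle-1 DLT**

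| Event | Outcome under the text |
|---|---|
| Non-hematologic, grade 3 or higher, not a grade 4 infection or hemorrhage; cleared only at day 29 or 36 | Meets 9.5; full dose is ordered |
| Same event, cleared by day 22 | Meets 9.5; next course given, no reduction provided for |
| Same event, not cleared by day 36 | Removed, unless CR or PR is already documented; then 9.8, which again requires the re-treatment criteria to be met |
| Grade 4 infection or hemorrhage | Fails 9.5 even if it resolves |
| Platelets below 75,000 to about day 36 | Fails the 75,000 threshold in 9.5, except in phase II patients enrolled at 50,000, whose threshold is 50,000 |

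The gap is in the first two rows, for patients without a documented PR or CR.

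**Expected cycle-1 DLTs among the 18 phase II patients**

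Inputs: 18 patients, of whom 6 are the phase I patients at the MTD (section 14.6: stage 1 of 8 is reached by adding 2); at most 1 DLT among those 6 (section 14.4.2); DLT incidence at the MTD below 33% (section 14.5). The true risk p is not given, so I take 0.10 to 0.30.

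For the 6 phase I patients, given at most 1 DLT:

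E = P(1) / [P(0) + P(1)] = 6p(1−p)^5 / [(1−p)^6 + 6p(1−p)^5] = 6p / (1 + 5p)

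For the other 12 patients, the expected number is 12p.

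| p | First 6 | Other 12 | Total of 18 |
|---|---|---|---|
| 0.10 | 0.60/1.50 = 0.40 | 1.2 | 1.6 |
| 0.20 | 1.20/2.00 = 0.60 | 2.4 | 3.0 |
| 0.30 | 1.80/2.50 = 0.72 | 3.6 | 4.3 |

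As a cross-check, 1 DLT observed in 6 at the MTD gives 1 + 12 × 1/6 = 3.0. A risk of 0.30 is not far-fetched: such a level still shows at most 1 DLT in 6 with probability 0.1176 + 0.3025 = 0.42.

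**Patients affected.** The share of DLTs that are non-hematologic, not barred by 9.5 and resolved by day 36 is not in the documents. Assuming 25% to 100%: low end 1.6 × 0.25 = 0.4; high end 4.3 × 1 = 4.3.

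**Size of one step down in Table 9.0 (mg/m²/day)**

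| From | To | Reduction |
|---|---|---|
| 49 | 36 | 26.5% |
| 36 | 28 | 22.2% |
| 28 | 20 | 28.6% |
| 20 | 13.2 | 34.0% |
| 13.2 | 8 | 39.4% |
| 8 | 4 | 50.0% |

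Level 1 (4 mg/m²/day) has no lower level.

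**The case against.** Several counter-arguments have force.

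- **Safeguards exist.** Toxicity review and examination precede every cycle, re-treatment requires recovery to grade 1 or baseline, and 13.0 lets the investigator stop. This stands, but stopping is not a lower dose.
- **An earlier response is conceivable.** Section 9.8 accepts a clinical response, and item 10.3 speaks of assessment or reassessment. That leaves a narrow opening before cycle 2, but no response assessment is scheduled then.
- **The subgroup may be small.** Section 5.2 expects DLT to take the form of delayed count recovery, and reports that non-hematologic toxicity in earlier solid-tumor and lymphoproliferative patients was infrequent and mild. The same section reports grade 3 non-hematologic events in leukemia patients at higher doses, and grade 3 or 4 infection in 94 of 377 patients (25%). The subgroup is not empty, but the upper end of the range should not be taken as likely.
- **The response condition looks deliberate.** It is written in both 9.5 and 9.8. Even so, neither section gives a reason for denying the lower dose to a recovered patient whose response has not yet been assessed.

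A reader might infer that the plan has no toxicity-driven reduction at all. The documents do not support that: 9.5 sends responders who have not recovered by day 36 to 9.8. That route does not reach a DLT that has resolved. A reader might also infer that the full dose is ordered at day 22. The instruction covers re-treatment after a delay only; section 4.3 is conditional on toxicity criteria it does not define, so the same dose at day 22 is implied, not stated.

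**Conclusion.** The concern holds for one group: patients with a cycle-1 non-hematologic DLT of grade 3 or higher, other than a grade 4 infection or hemorrhage, that resolves in time for re-treatment, and without a documented PR or CR. For them the plan offers the same dose or removal. After a delay the same dose is explicit; at day 22 it follows from the absence of any other provision.

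In phase II the expected number is about 0.4 to 4.3 of 18. This rests on an assumed true DLT risk of 0.10 to 0.30 and an assumed affected share of 25% to 100%. The top is an upper bound, since it needs every DLT to be of the affected kind.

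Phase I patients fall under the same rules, but the documents do not allow a count. A level declared above the MTD has at least 2 patients with a DLT, and one might infer that at least 2 are affected there. That does not follow: those DLTs may be prolonged thrombocytopenia or grade 4 infection, which 9.5 already stops. Nor do the documents show that patients who tolerated cycle 1 at such a level must be reduced.

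This is a correctable safety gap. It does not undermine the MTD determination or the phase II decision rule.

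**What to change.** - **Section 9.8:** add that a patient without progression who had a drug-related non-hematologic DLT event of grade 3 or higher, and who meets the re-treatment criteria, is re-treated at the next lower level of Table 9.0 regardless of response. At level 1, whether to continue or stop is the investigator's decision under 13.0.
- **Section 9.5:** limit the full-dose instruction to patients without such an event.
- **Section 14.6:** state that patients count by starting dose in the rule requiring 4 responses among 18.

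Keep the day-36 limit, the bar for grade 4 infection and hemorrhage, and DLT and MTD determination on cycle 1.

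The cost is a few sentences, with no added patients, visits or tests. The downside is a dose 22% to 50% lower from cycle 2, depending on level, in a few patients, which could slightly lower the observed response rate. Counting by starting dose puts some reduced-dose cycles into the response estimate, but 9.8 already allows that for responders. A permissive sentence, allowing the reduction without requiring it, would be a smaller change, but would leave the dose after a DLT to individual judgment.
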